
- Removal of the requirements for mean platelet volume and hemoglobin A1c testing from [Attachment 2](#) (Clinical Laboratory Tests) and a change in the coagulation testing from central collection to performance at the local laboratory.
- Addition of a Cycle 4 Day 1 olaratumab pharmacokinetic (PK) sample to [Attachment 4](#), as well as minor edits for clarity.
- Minor editorial revisions for clarity throughout the protocol.

The amended JGDQ(a) protocol will be the first version of the protocol operationalized at investigative sites.

5.1.2. *Rationale for Amendment (b)*

As of 21 September 2017, 2 of 4 patients enrolled in Cohort 1 had asymptomatic lipase increases (Grade 4) without any clinical or radiographic signs of pancreatitis. Asymptomatic lipase and amylase increases have been reported in patients treated with immuno-oncology agents (Postow 2015; Villadolid and Amin 2015; Bender et al. 2016). A 2015 review showed Grade ≥ 3 lipase increases were reported in multiple studies of immuno-oncology agents, ranging from an incidence of 1% to up to 13% (Naidoo et al. 2015). This review included a total of 16 patients with Grade ≥ 3 lipase increases, while other studies not included in this review provide further reports of lipase increases (Bender et al. 2016; Hamid et al. 2017). Based on observations of patients with \geq Grade 3 asymptomatic lipase and amylase elevations, recently published recommendations suggest that no modification to treatment is indicated in such patients and that these laboratory parameters should not even be routinely tested due to lack of clinical consequence (Postow 2015; Fay et al. 2016; Hofmann et al. 2016).

However, per Study JGDQ protocol version (a), these Grade 4 lipase elevations qualified as DLTs, resulting in 2 patients with DLTs out of 4 enrolled and enrollment was, therefore, stopped.

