Following discussions with the investigators and with Merck, this amendment revises the treatment modification guidelines to allow patients with clinically non-significant, treatable, or reversible lipase or amylase elevations to continue to receive study treatment. In addition, the DLT criteria have been updated to reflect the most current wording for pembrolizumab protocols including that non-hematologic laboratory elevations that are deemed clinically non-significant or are treatable/reversible would not be considered a DLT, nor in certain situations Grade 3 rash and Grade 3 fatigue are not considered DLTs. The rationale for this change regarding non-hematologic laboratory abnormalities is discussed above in this section; the revised DLT criteria are described in [Section 7.2.2.2](#) and the revised dose modifications are described in [Section 7.2.4](#). Based upon these protocol revisions, Lilly intends to enroll 1 to 3 additional patients at the first dose level to adequately determine the safety of the combination at this dose level.

In addition, minor editorial changes have been made throughout the protocol to improve clarity and practicability of the protocol, secure alignment with the intended study design, and update information available for study drugs.

5.1.3. *Rationale For Amendment (c)*

Protocol Amendment (c) for Study JGDQ adds the ability for pembrolizumab to be supplied for the study as an aqueous solution in addition to the lyophilized powder formulation.

The amendment also adds an exclusion criterion for patients that have had an allogenic tissue or solid organ transplant, consistent with other pembrolizumab clinical trials. Moreover, it clarifies data collection requirements intended for the follow-up period.

Amendment (c) also includes an update to the olaratumab premedication instructions.

Minor editorial changes have been made throughout the protocol to improve clarity and practicability of the protocol, secure alignment with the intended study design, and update information available for study drugs.

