7.2.2.2. Dose-Limiting Toxicity Determination

A DLT is defined as an AE during Cycle 1 that is possibly related to the study drug and fulfills any 1 of the following criteria using the NCI CTCAE v4.0:

- CTCAE Grade ≥ 3 nonhematologic toxicity. Exceptions that will not be considered a DLT are:
 - Grade 3 nausea, vomiting, diarrhea, or constipation that lasts ≤ 72 hours and that can be controlled with appropriate treatment; Grade 3 fatigue that lasts ≤ 72 hours; Grade 3 rash without the use of corticosteroids or anti-inflammatory agents per standard of care
 - Clinically non-significant, treatable, or reversible laboratory abnormalities including liver function tests, pancreatic enzymes, uric acid, electrolytes, etc. Grade 4 electrolyte disturbance lasting more than 24 hours despite appropriate treatment will be considered a DLT.
 - Transient (<7 days) Grade 3 elevations of alanine aminotransferase (ALT) and/or aspartate aminotransferase (AST) that are not accompanied by a Grade 2 bilirubin increase are considered an exception to the DLT criteria, unless there is a clear alternative cause (for example, worsening biliary obstruction) if agreed by the study investigator and Lilly CRP/CRS.
 - Grade 3 endocrine disorder (thyroid, pituitary, and/or adrenal insufficiency) that is managed with or without systemic corticosteroid therapy and/or hormone replacement therapy and the patient is asymptomatic

- Grade 3 inflammatory reaction attributed to a local antitumor response (for example, inflammatory reaction at sites of metastatic disease, lymph nodes, etc.)
- Concurrent vitiligo or alopecia of any AE grade
- Any infusion or hypersensitivity reactions occurring during the infusion of the drug are not considered dose-related and therefore will NOT be considered a DLT
- Grade 4 anemia
- Grade 4 neutropenia or leukopenia of >5 days duration
- Any febrile neutropenia
- Grade 3 thrombocytopenia with clinically significant bleeding or Grade 4 thrombocytopenia
- Any other significant toxicity deemed by the primary investigator and Lilly clinical research personnel to be dose limiting (for example, any toxicity that is possibly related to the study medication that requires the withdrawal of the patient from the study during Cycle 1)

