7.2.4.1.2. Nonhematologic Toxicity

Specific guidelines for dose adjustments in patients who experience olaratumab IRRs may be found in Section 7.5.1.1.

General guidelines for dose modification for other nonhematologic toxicities related to olaratumab are shown in Table JGDQ.3. If more than 2 toxicity-related olaratumab dose reductions are required, olaratumab will be permanently discontinued.

Table JGDQ.3. General Guidelines for Dose Modification Due to Nonhematologic Toxicities Related to Olaratumab

Reaction Grade	Required Dose Modification
Grade 1	No dose modification is required.
Grade 2	At the investigator's discretion, the patient may continue to receive olaratumab per protocol, provided that the event does not pose a serious health risk or is easily treated.
Grade 3	For a Grade 3 toxicity not adequately controlled with appropriate supportive care, the dose must be withheld until toxicity is \leq Grade 1 or has returned to pretreatment baseline; then treatment may resume at a reduced dose of 12 mg/kg for the 15-mg/kg cohort (Phase 1a) and reduced dose of 15 mg/kg for the 20-mg/kg cohort. If toxicity recurs after therapy resumes, a second dose reduction (second dose reduction of 10 mg/kg for the 15-mg/kg cohort and 12 mg/kg for the 20-mg/kg cohort) is permitted.
Grade 4	The dose must be withheld until dose toxicity is \leq Grade 1 or has returned to baseline. Permanent discontinuation should be considered for any patient experiencing Grade 4 nonhematologic toxicity assessed as related to olaratumab. However, if resumption of dosing is deemed appropriate by the investigator, treatment may resume only after consultation with the Lilly study physician, with the dose reduced to 10 mg/kg for the 15-mg/kg cohort or to 15 mg/kg for the 20-mg/kg cohort. If Grade 4 toxicity recurs after therapy resumes, all study treatment will be discontinued.

Note: for asymptomatic Grade 3/4 laboratory abnormalities that are clinically non-significant, treatable, or reversible, treatment with olaratumab may continue without dose modifications at the discretion of the investigator.

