Hypothyroidism	Grade 2-4	Continue	Initiate thyroid replacement hormones (eg, levothyroxine or liothyronine) per standard of care	Monitor for signs and symptoms of thyroid disorders.
Nephritis and Renal dysfunction	Grade 2	Withhold	Administer corticosteroids (prednisone 1-2 mg/kg or equivalent) followed by taper.	Monitor changes of renal function
	Grade 3 or 4	Permanently discontinue		
Myocarditis	Grade 1 or 2	Withhold	Based on severity of AE administer corticosteroids	Ensure adequate evaluation to confirm etiology and/or exclude other causes
	Grade 3 or 4	Permanently discontinue		
All other immune-related AEs	Intolerable/ persistent Grade 2	Withhold	Based on type and severity of AE administer corticosteroids	Ensure adequate evaluation to confirm etiology and/or exclude other causes
	Grade 3	Withhold or discontinue based on the type of AE		

		event. Events that require discontinuation include and not limited to: Guillain-Barre Syndrome, encephalitis		
	Grade 4 or recurrent Grade 3	Permanently discontinue		

¹ Withhold or permanently discontinue pembrolizumab is at the discretion of the investigator or treating physician.

NOTE:

For participants with Grade 3 or 4 immune-related endocrinopathy where withhold of pembrolizumab is required, pembrolizumab may be resumed when AE resolves to \leq Grade 2 and is controlled with hormonal replacement therapy or achieved metabolic control (in case of T1DM).

Abbreviations: AE = adverse event; ALT = alanine aminotransferase; AST = aspartate aminotransferase; CTCAE = Common Terminology Criteria for Adverse Events; GI = gastrointestinal; irAE = immune-related adverse event; IV = intravenous; T1DM = Type 1 diabetes mellitus.

Note: Patients who have asymptomatic or clinically non-significant Grade 3 or 4 lipase or amylase elevations (that is, not associated with clinical symptoms or radiological signs of pancreatitis) which are transient as demonstrated by a decrease of at least 1 CTCAE Grade within 7 days ± 3 days of onset will not require pembrolizumab discontinuation or modification. If the elevation has not decreased at least 1 CTCAE Grade within this time window, pembrolizumab treatment may only continue after consultation and discussion with the Sponsor.

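### The laboratory exemption from the DLT count is wider than the limits in Tables JGDQ.3 and JGDQ.4, so an event that permanently ends pembrolizumab can leave the patient counted as evaluable and DLT-free

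*Protocol*

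**What the plan says.** Under Section 7.2.2.2 of the protocol, a possibly related nonhematologic toxicity of Grade 3 or higher in Cycle 1 is a DLT, subject to listed exceptions. One exception reads "Clinically non-significant, treatable, or reversible laboratory abnormalities including liver function tests, pancreatic enzymes, uric acid, electrolytes, etc". A single qualification follows: "Grade 4 electrolyte disturbance lasting more than 24 hours despite appropriate treatment will be considered a DLT". A separate bullet exempts Grade 3 ALT/AST rises lasting under 7 days without a Grade 2 bilirubin increase.

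Section 5.1.2 (rationale for Amendment (b)) describes the change in the same sense: "non-hematologic laboratory elevations that are deemed clinically non-significant or are treatable/reversible would not be considered a DLT". The trigger was that "2 of 4 patients enrolled in Cohort 1 had asymptomatic lipase increases (Grade 4) without any clinical or radiographic signs of pancreatitis". The supporting literature is summarised as concerning "asymptomatic lipase and amylase elevations, recently published recommendations suggest that no modification to treatment is indicated in such patients".

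The dose-modification text is narrower. The note to Table JGDQ.3 (olaratumab) lets treatment continue unmodified "for asymptomatic Grade 3/4 laboratory abnormalities that are clinically non-significant, treatable, or reversible". The note to Table JGDQ.4 (pembrolizumab) covers "asymptomatic or clinically non-significant Grade 3 or 4 lipase or amylase elevations", explained as having no symptoms or radiological signs of pancreatitis, and it also requires a fall of at least one grade within 7 ± 3 days. In the body of Table JGDQ.4, pembrolizumab is permanently discontinued for immune-related Grade 3 or 4 AST/ALT or bilirubin elevation, and for Grade 3 or 4 nephritis and renal dysfunction.

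**The concern.** The three descriptions in the exemption are alternatives. Read literally, a clinically significant Grade 3 or 4 laboratory value is exempt if it can be treated or if it reverses. The neighbouring exceptions in Section 7.2.2.2 are bounded by grade, duration or absence of symptoms; this one is bounded only for Grade 4 electrolytes. The evidence offered for it concerns asymptomatic lipase and amylase rises, but the exemption reaches laboratory tests in general.

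The same event can therefore be outside the DLT count and yet be one for which the protocol's own table ends a study drug. With three to six patients per dose level and a limit of one DLT in six, the classification of one or two events can change whether the DLT rule is met. DLETs are defined by the same criteria, so later-cycle events inherit the gap.

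**Working it through.** **Passages side by side**

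| Feature | 7.2.2.2 exemption | Table JGDQ.3 note | Table JGDQ.4 note |
|---|---|---|---|
| Tests covered | laboratory tests in general | laboratory tests in general | lipase and amylase only |
| Symptom limit | none | asymptomatic only | asymptomatic or non-significant, without symptoms or radiological signs of pancreatitis |
| Time limit | none, except Grade 4 electrolytes over 24 hours | none | fall of at least 1 grade in 7 ± 3 days |
| Effect | not a DLT | olaratumab may continue unmodified | pembrolizumab may continue unmodified |

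**How an event that ends one drug can be DLT-free**

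1. Take a related, immune-related Grade 3 or 4 bilirubin rise in Cycle 1 that can be treated or reverses. Liver function tests are named in the exemption, so it need not be a DLT.
2. Table JGDQ.4 permanently discontinues pembrolizumab for it.
3. Section 6.3.2 lets the patient continue the other drug. Pembrolizumab is given only on Day 1 (Section 7.2.1.2), so no Cycle 1 dose of it remains to be missed.
4. If olaratumab continues through Cycle 1, the patient has completed the cycle and can be counted as evaluable and DLT-free.
5. If all study treatment stops before Cycle 1 is complete and no DLT is declared, Section 7.6.1 makes the patient non-evaluable and replaceable. The event then leaves the denominator instead of counting as DLT-free.

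For ALT/AST, the narrower bullet (Grade 3, under 7 days) overlaps the general one, and the protocol does not say which governs. Even under the narrower bullet, an immune-related Grade 3 rise can be exempt while Table JGDQ.4 stops pembrolizumab.

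**The plan's own figures**

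Under Section 7.2.2.1, 2 DLTs at Dose Level 1 stop the regimen, and at most 1 of 6 lets the study proceed. 1/6 = 16.7% and 2/6 = 33.3%, which agrees with the MTD definition of below 33%. In Section 5.1.2, 2 of 4 patients had DLTs under the previous criteria; the same two events, if exempt, contribute 0 of 4.

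**Illustration with assumed rates**

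The documents give no rate for exempt events. Assume other DLTs in 20% of patients and exempt laboratory events in a further 10% or 15%, with no overlap and patients independent. A dose level passes with 0 of 3, or with 1 of 3 followed by 0 of 3:

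P(pass) = (1−p)³ + 3p(1−p)⁵

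- p = 0.20 (exempted): 0.512 + 0.6 × 0.3277 = 0.71
- p = 0.30 (10% counted): 0.343 + 0.9 × 0.1681 = 0.49
- p = 0.35 (15% counted): 0.2746 + 1.05 × 0.1160 = 0.40

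At least six patients are required at the highest tolerated dose. For six evaluable patients there, P(at most 1 of 6) = (1−p)⁶ + 6p(1−p)⁵ gives 0.66, 0.42 and 0.32 at the same three rates.

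The assumed share can be varied instead. With a true rate of 33% when every event is counted, the 3+3 pass probability is 0.43. If 25%, 50% or 75% of those events are exempt, it becomes 0.61, 0.78 or 0.93.

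**The case against.** The case for leaving the text alone has real substance.

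- The *or* is deliberate. Section 5.1.2 repeats it, says the amendment followed discussion with the investigators and the partner company, and presents the criteria as current wording for pembrolizumab protocols. A reader might infer a drafting slip; the documents do not support that.
- DLT status and dose modification are separate by design. Section 7.2.4.1 plans for toxicities that are not DLTs but still require omitted doses, and it allows replacement of a patient whose Cycle 1 dose is adjusted or delayed. A held dose without a DLT is therefore no contradiction in itself.
- The exemption covers laboratory abnormalities. A symptomatic clinical event of Grade 3 or higher, such as pancreatitis, can still be a DLT in its own right.
- The word-for-word contrast on symptoms is clean only against Table JGDQ.3. Creatinine is not named in the exemption, so the renal row of Table JGDQ.4 is a weaker example than the liver row.
- There are backstops. Section 7.2.2.2 has a catch-all criterion, and it says all available safety data, including later cycles, will be considered. Section 7.2.2.1 requires documented agreement before escalation. SAP Section 6.13.4 summarises laboratory grades by cohort and dose level, so exempt events are not hidden.

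These points narrow the concern but do not remove it. The catch-all is discretionary, and its example is withdrawal from the study, not loss of one drug. The wider review is required, but no rule says how exempted events weigh in it. SAP Section 6.13.2 lists DLTs and DLT-equivalent toxicities without a tally of exempted events; the SAP (February 2017) predates Amendment (b) (November 2017).

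**Conclusion.** The concern holds in a limited form. As written, the DLT exemption is broader than the two dose-modification notes and broader than the evidence cited for it. An event for which Table JGDQ.4 permanently ends pembrolizumab can be left out of the DLT count, with the patient evaluable and DLT-free on olaratumab.

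Three stronger readings are tempting and should not be drawn. First, that any toxicity ending study treatment can count as DLT-free: Section 7.6.1 makes a patient who stops all treatment in Cycle 1 without a DLT non-evaluable. Second, that one reclassified event mechanically decides escalation: the protocol requires a broader safety review and agreement. Third, that the two lipase events behind Amendment (b) were wrongly reclassified: they were asymptomatic, and the point here is only that the wording reaches further than they do.

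The size depends on assumed rates. On the 3+3 rule with other DLTs at 20%, exempting events in a further 10% to 15% of patients raises the pass probability from 0.49 or 0.40 to 0.71. The direction follows from the rule; the amount cannot be fixed from the documents. The figures also assume that no DLT is declared under the catch-all and that the wider review does not change the decision.

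**What to change.** Reconcile Section 7.2.2.2 with the notes and actions in Tables JGDQ.3 and JGDQ.4. State whether the asymptomatic limit applies to the DLT exemption, and how a laboratory event that requires permanent discontinuation of one drug is counted when the other continues. Which clinical rule to adopt is for the sponsor and investigators; this review proposes none.

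At each cohort review, show the DLT count twice: as defined, and with laboratory-exempted Grade 3/4 events added. Add the same display to SAP Section 6.13.2.

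The cost is a short clarification in the protocol and one extra line per cohort review. The downside is that, depending on the rule chosen, an occasional laboratory event may become a DLT.

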7.2.3. Phase 1b Dose Expansion

Based on the safety profile observed during the Phase 1a portion of the trial, the sponsor will determine the dosing regimen to be investigated in the Phase 1b portion of the study and open enrollment in the Phase 1b portion to further evaluate the combination therapy in this patient population.

Patients enrolled to the Phase 1a portion of the study will not participate in the Phase 1b portion. Patients in Phase 1b portion will meet the same eligibility criteria as for Phase 1a portion of the study. The purpose of Phase 1b expansion is to gather additional safety, tolerability, pharmacokinetics (PK) and pharmacodynamics (PD), and preliminary efficacy information regarding the combination.

7.2.4. Dose Adjustments and Delays

7.2.4.1. Olaratumab

Olaratumab dose adjustments within Cycle 1 should be avoided if possible. If a dose adjustment or delay is required during Cycle 1 in the dose-escalation phase of the study, the patient will be allowed to continue but may be replaced if deemed appropriate by the Lilly CRP/CRS and investigator.

If a patient treated at a given dose level experiences a DLT (as defined in Section 7.2.2.2), then treatment will be suspended for that patient. Dosing may restart after recovery from toxicity at a lower dose after consultation between the investigator and Lilly CRP/CRS. If a toxicity does not meet the criteria for a DLT in Cycle 1 (or a DLET) but nonetheless requires omission of dose(s) for tolerability, then dosing may resume at the same dose or reduced dose after the toxicity resolves to baseline; however, the dose(s) omitted for tolerability during a cycle will not be replaced. Treatment may be delayed for up to 14 days to allow a patient sufficient time for recovery from study drug-related toxicity. If Day 8 dosing is delayed for approximately 14 days, the patient should resume treatment with Day 1 treatment for the next cycle.

The olaratumab dose for a patient should be reduced for all subsequent cycles of therapy, if the investigator determines that it is in the best interest of the patient or if the patient experienced at a DLT. For such patients requiring a dose reduction, re-escalation to the original dose level is not permitted. Patients who require more than 2 dose reductions of olaratumab will be discontinued from olaratumab treatment. If a patient experiences a DLET at a reduced dose level, then the patient will be discontinued from study treatment.

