Investigators, together with the Lilly CRP/CRS, can declare a DLT if a patient is experiencing increasing toxicity during further cycles of treatment and it becomes clear that it will not be possible to continue on treatment without exposing the patient to excessive risk.

A dose-limiting equivalent toxicity (DLET) is an AE that meets the DLT criteria as defined above and occurs in any cycle other than Cycle 1 for a patient enrolled in the Phase 1a portion of the study.

The MTD is defined as the highest tested dose that has <33% probability of causing a DLT during Cycle 1. At the time of safety assessments for each cohort, all available safety data, including DLTs and DLETs from later cycles of treatment, will be included. In addition to the DLT assessment period in Cycle 1, safety data beyond Cycle 1 available at the time of safety review will also be taken into consideration prior to determining dose escalation, whether to enroll additional patients, or whether to proceed to the Phase 1b portion of the study.

Toxicity that is clearly and directly related to the primary disease or to another etiology is excluded from the definition of DLTs.

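### Section 7.2.4.1 and the Grade 3 row of Table JGDQ.3 set different olaratumab restart rules for the same non-DLT, non-DLET toxicity, and the protocol does not say which governs

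*Protocol*

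**What the plan says.** Two places in the protocol tell a site when, and at what dose, olaratumab may be restarted.

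Section 7.2.4.1 sets its scope by DLT status: "If a toxicity does not meet the criteria for a DLT in Cycle 1 (or a DLET) but nonetheless requires omission of dose(s) for tolerability". For such an event the section gives this restart rule: "then dosing may resume at the same dose or reduced dose after the toxicity resolves to baseline". The same section ties dose reduction to clinical judgment or to a DLT: "The olaratumab dose for a patient should be reduced for all subsequent cycles of therapy, if the investigator determines" that this serves the patient, or if a DLT has occurred. A reduced dose may not be raised again. Delay for recovery is allowed for up to 14 days.

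Section 7.2.4.1.2 sets its scope by type of toxicity and by cause: "General guidelines for dose modification for other nonhematologic toxicities related to olaratumab are shown in Table JGDQ.3". Infusion-related reactions are handled elsewhere. The Grade 3 row opens "For a Grade 3 toxicity not adequately controlled with appropriate supportive care, the dose must be withheld until toxicity is" at or below a stated level. It gives that level and the restart dose as "Grade 1 or has returned to pretreatment baseline; then treatment may resume at a reduced dose of 12 mg/kg for the 15-mg/kg cohort (Phase 1a"). The entry for the 20-mg/kg cohort is 15 mg/kg. The row has no same-dose option. A note under the table lets treatment continue unmodified for certain symptom-free laboratory abnormalities. The table's title calls its contents general guidelines, while its column heading calls the modification required.

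Section 7.2.2.2 defines a DLT by Cycle 1. It defines a DLET as an event that meets the DLT criteria and "occurs in any cycle other than Cycle 1 for a patient enrolled in the Phase 1a portion of the study". It also lets investigators and the sponsor declare a DLT in a later cycle.

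**The concern.** One event can fall under both rules, and the rules differ on two things: how far the toxicity must resolve, and whether the full dose may be given again. A site that follows one passage may restart a patient in a way that the other does not allow.

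Two things are at stake. The first is re-exposure of patients after a serious toxicity under a rule that the protocol also contradicts. The second is the data. Safety and tolerability are the Phase 1b primary objective, and SAP Section 6.13.1 summarizes omissions, reductions, cycle delays and percent dose intensity. Protocol Section 10.1.1 says that the recommended dose may be revised on Phase 1b safety data. If sites resolve the conflict differently, part of the variation in those summaries comes from the wording and not from the drug.

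**Working it through.** The protocol states no figure to reproduce. The check is a comparison of the two passages, with simple arithmetic on the doses.

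**Step 1. Which events fall under both rules?** Section 7.2.4.1 needs an event that is neither a DLT nor a DLET and that leads to omitted doses. The Grade 3 row needs an event that is nonhematologic, related to olaratumab, not an infusion-related reaction, not brought under control by supportive care, and outside the laboratory note. The overlap is the set that meets all of these.

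- Phase 1a: such an event would ordinarily be a DLT or DLET, so the overlap is small.
- Phase 1b, Cycle 1: unclear. The DLT definition sits under the Phase 1a heading but does not itself name Phase 1a. If it applies, the DLT sentence in Section 7.2.4.1 already calls for a lower dose.
- Phase 1b, after Cycle 1: a DLET is not possible by definition, and the event is not a DLT unless one is declared. Both rules then apply. This is the clearest case.

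**Step 2. The two rules side by side for that case.**

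| | Section 7.2.4.1 | Table JGDQ.3, Grade 3 row |
|---|---|---|
| Recovery needed | Baseline | Grade 1 or lower, or baseline |
| Restart dose | Same or reduced | Reduced |

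**Step 3. When do the thresholds differ?** With baseline Grade 0, the text needs Grade 0 and the table accepts Grade 1. With baseline Grade 1 or higher, a return to baseline satisfies both, and the thresholds coincide. The threshold conflict therefore exists only for baseline Grade 0. The dose conflict does not depend on baseline grade.

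**Step 4. How far apart are the doses?** Olaratumab is given on Days 1 and 8, so there are two doses per 21-day cycle.

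- 20-mg/kg cohort: same dose 2 × 20 = 40 mg/kg per cycle; reduced 2 × 15 = 30. Difference (40 − 30)/40 = 25%.
- 15-mg/kg cohort: same dose 2 × 15 = 30; reduced 2 × 12 = 24. Difference (30 − 24)/30 = 20%. The table labels this entry Phase 1a, so whether it applies to a Phase 1b cohort at 15 mg/kg is itself unclear.

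SAP Section 6.13.1 defines percent dose intensity as 100 × actual/planned cumulative dose. If the planned dose stays at the assigned level (an assumption), each full cycle after a reduced restart scores 100 × 30/40 = 75% or 100 × 24/30 = 80%, against 100% after a same-dose restart.

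**Step 5. Can a site satisfy both?** Yes, by waiting for baseline and then restarting at the reduced dose. A restart at Grade 1 from baseline Grade 0 follows the table and breaches the text. A same-dose restart at baseline follows the text and breaches the table.

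**Step 6. How many patients?** Phase 1b plans about 25, so one patient is 1/25 = 4%. The documents give no rate for the event defined in Step 1, so no count can be derived.

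**The case against.** The strongest reply is structural. Table JGDQ.3 sits in a subsection of 7.2.4.1, so the parent text can be read as the general rule and the table as the specific one. The parent text is also permissive: it already includes a reduced dose among its options. On this reading the only defect is a missing precedence sentence.

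Part of this stands. The rules are not mutually exclusive, as Step 5 shows. But the protocol states no precedence, and neither scope contains the other: one is drawn by DLT status, the other by grade, type and cause. The reading also has an odd result. The Grade 2 row speaks only of continued dosing, so the parent text would still govern a Grade 2 event that needs omission. With baseline Grade 0, that event would have to clear fully, while a Grade 3 event could restart at Grade 1. The protocol does not explain that ordering.

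It is also fair to reply that the study is single-arm and descriptive, with no hypothesis test (SAP Section 6.5), and that dose adjustments are reported with reasons. No formal inference is at risk.

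Three stronger readings are tempting and are not supported:

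- A reader might infer that the conflict covers Phase 1b Grade 3 toxicity in general. The table's conditions and the option to declare a DLT make it narrower.
- A reader might infer from the 14-day limit that a lingering Grade 1 residual decides between restart and discontinuation. Section 7.2.4.1 does not make a longer delay a reason to discontinue. The schedule footnote on visit windows in Attachment 1 allows longer delays in later cycles after consultation.
- A reader might apply an overall Grade 3 rate to the 25 patients. That would overcount, because the trigger is only a subset of Grade 3 events.

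**Conclusion.** The inconsistency is real but narrow. For an uncontrolled, olaratumab-related, nonhematologic Grade 3 toxicity that is neither a DLT nor a DLET, the two passages can lead to different restart times (only with baseline Grade 0) and to restart doses that differ by 25% or 20%. They need not do so, since one course of action satisfies both. The case is firmest in Phase 1b after Cycle 1, provided that no late DLT is declared. The 20% figure also rests on applying to Phase 1b an entry labelled Phase 1a. The number of patients is unknown and likely small. The point matters for consistent handling of re-exposure and for clean tolerability summaries. It does not undermine the study's conclusions.

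**What to change.** Reconcile Section 7.2.4.1 with Table JGDQ.3. State which passage governs for which grade and type of toxicity, so that each event has one recovery threshold and one restart-dose rule. Say explicitly what applies in Phase 1b, including whether the entry labelled Phase 1a extends to a 15-mg/kg expansion cohort. Which threshold and restart dose to adopt is a decision for the sponsor's physicians. The cost is a wording change at the next amendment or a clarification letter to sites, with no added data or procedures.
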